The study will end at once if severe adverse events associated with CHM occurs or sufficient evidence indicates that adding CHM is not superior to the SMT group. Besides, CHM will discontinue and the final status will be censored in the condition of liver transplantation or the onset of liver cancer. Allocated interventions can be changed upon participant's request. All these changes will be recorded and analyzed based on intention-to-treat (ITT).

Intervention

Standard medical treatment

The SMT include a high-calorie diet; nucleoside analogues for HBV DNA-positive patients; sodium restriction, diuretics and paracentesis combined with albumin infusion for ascites; lactulose and L-ornithine aspartate and lactulose for HE and hyper-ammonia; hemostatic treatment for gastrointestinal hemorrhage; antibiotics for infections and renal replacement for HRS and uremic symptoms. CHM formulas, whatever routes of administration, are prohibited in the SMT group.

Chinese herbal medicine formula

There are two kinds of CHM based on traditional Chinese Medicines (TCM) syndromes. The common components of the two CHM formulas include *Artemisiacapillaris* Thunb (30g), *Salvia miltiorrhiza* Bge (30g), *Rhizoma*

Atractylodis Macrocephalae (30g), Rubia cordifolia L (30g), Sieyesbeckiaorientalis L (30g). Additional four components of Paeoniae Radix Rubra (60g), Gardenia jasminoides Ellis (9g), Hedyotis diffusa Willd (30g), Bletilla striata (15g) are involved for excess syndrome, and five other components of Astragalus membranaceus (30g), Radix Pseudostellariae (15g), Radix Aconiti Lateralis Praeparata (10g), Galli Gigeriae Endothelium Corneum (20g), Polygonum cuspidatum Sieb.et Zucc (15g) are involved for deficiency syndrome. All ingredients are manufactured as a Chinese herbal granule in a specific weight ratio to the raw herb (Beijing Kang Rentang Pharmaceutical Co., Ltd, Beijing, China) in accordance with the quality criteria of Chinese pharmacopoeia in 2015. Patients will take one dosage of CHM granule per day for 8 weeks. For patients who cannot take oral medicine can be switched to colon route by the colonic therapy system (IMS-100A produced by Sunny Medical in Beijing China).

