In addition, patients in the CHM group will also receive daily herbal enema of 100 microliter decoction composed by Radix et Rhizoma Rhei Palmati (Dahuang) 30g and Fructus Mume (Wumei) 30g for 7 days expect the following contraindications: (1) severe hemorrhoid, (2) female patients during menstruation, (3) anal stenosis, (4) artificial anal and (5) cardiac disease.

Outcome measurements

Primary outcome

The primary outcome is transplant-free survival at week 12.

Secondary outcomes

Secondary outcomes include (1) transplant-free survival at week 24, (2) the influence on liver function assessed by MELD score (involving levels of serum bilirubin, creatinine, INR and sodium) at week 12, (3) the influence on liver function assessed by Child-Pugh score (involving the serum bilirubin, coagulation function, albumin and the complication of hepatic encephalopathy and ascites) at week 12. (4) quality of life assessed by WHOQOL-BRIEF at week 12 and (5) the incidence of serious complications (including infections, encephalopathy, HRS, and gastrointestinal bleeding) from week 1 to week 24.

Safety outcomes

Primary vital signs, physical examinations, electrocardiogram and some laboratory tests such as routine blood test, urine test, renal function will be assessed before and after treatment to monitor the safety of this study. Furthermore, adverse events are also recorded in a predesigned case report form (CRF) through the whole study period. An independent safety committee will analyze the incidence and severity of adverse events to identify any unexpected adverse events or mortality in the CHM groups.

Other assessed parameters

Epidemiological characteristics, the details of nucleoside/nucleotide analog therapy, family history of liver disease were collected from patient medical record, the level of HBV DNA, endotoxin, and lymphocyte subsets were tested as well as CLIP-C-ACLF score were computed at week 24 and 48. The plasma level of HBV DNA, endotoxin, and cytokines were tested in ADICO clinical laboratories (Shanghai, China) which is blind to the allocation information. Remnant plasma will be stored at -80°C for ancillary studies. Women of childbearing age will undergo pregnancy test for the eligibility.

Sample size

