The proposed -12% superiority margin of 8-week mortality rate was chosen based on our previous results of 30.87% in the SMT group. Considering a power of 0.80 and 10% of attrition rate, 255 subjects are needed for each group to achieve the significance level of 0.05 in assessing the difference between the two groups.

Randomization

The eligible patients will be randomly allocated to the SMT group and CHM group in a 1:1 ratio. The sealed numbers are generated by a computerized random number generator with statistical analysis system (SAS) software by an independent statistician from the center of clinical evaluation in China Academy of Chinese medical sciences (Beijing, China) and are concealed using opaque envelopes.

Trial monitoring

Trial monitoring is assumed by an independent Contract Research Organization so as to verify that: (1) The rights and well-being of human subjects are protected. (2) The reported trial data are accurate, complete, and verifiable from source documents. (3) The conduct of the trial is in compliance with the currently approved protocol/amendment(s), with GCP, and with the applicable regulatory requirement(s). Monitors should be appropriately trained and have the scientific and/or clinical knowledge needed to monitor the trial adequately. A risk-based monitoring strategy is developed in this trial, which includes on-site and centralized monitoring, which is more likely than routine visits to all clinical sites and 100% data verification to ensure subject protection and overall study quality. On-site monitoring is an in-person evaluation carried out by the monitor at the sites at which the clinical investigation is being conducted. Centralized monitoring is a remote evaluation carried out at a location other than the sites at which the clinical investigation is being conducted. Key monitoring processes include subject inclusion process; implementation of the inclusion criteria; source data verification; data integrity, etc.

Data management and Statistical methods

Data entry will be conducted by two independent administrators using online electronic CRF for accuracy and consistency. At the end of the study, the database will be locked and analyzed under the agreement of principal investigator and statistician, who are privileged to access the final trial dataset.

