The randomized subjects who take at least one dose of CHM or SMT constitute the full analysis set (FAS) and those who complete all the visits constitute the per-protocol set (PPS). An efficacy assessment will be analyzed using FAS and PPS based on the principle of ITT. Subjects who have taken the CHM and been evaluated the safety at least once constitute the safety set (SS), which is used for safety evaluation. The statistical analysis will be performed using SAS 9.0 software (SAS Institute, Cary, NC, USA) by independent data management committee who are blind to the interventions.

Comparison of the two groups is conducted for the continuous variables with *t*-test and the categorical variables or rates with the chi-square test. The Kaplan-Meier overall survival curves will be generated and tested by log-rank. Cox proportional hazards regression model will be adopted to determine the prognostic factors associated with transplant-free survival. Multivariate logistic regression analyses will be adopted to explore factors associated with the incidence of liver-related complications. Subgroup analyses will be done based on the diagnostic criteria of Asian Pacific Association for the Study of the Liver (APASL) and European Association for the Study of the Liver (EASL) guideline.

The last observation carried forward approach was used for missing values. The statistical significance is defined as a two-sided $P < 0.05$.

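### If the safety set's evaluation requirement means a post-dose evaluation, treated patients who die first would leave its harm rates; exposure alone should define the set

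*Combined protocol and SAP*

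**What the plan says.** The section Data management and Statistical methods sets two joint conditions for the safety set: "Subjects who have taken the CHM and been evaluated the safety at least once constitute the safety set (SS". This is the set on which safety is to be analysed. The same paragraph sets only an exposure condition for the efficacy set: "The randomized subjects who take at least one dose of CHM or SMT constitute the full analysis set (FAS".

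The section Safety outcomes describes how safety is observed. Vital signs, physical examination, electrocardiogram and laboratory tests "will be assessed before and after treatment to monitor the safety of this study"; no on-treatment time is given. It adds that "adverse events are also recorded in a predesigned case report form (CRF) through the whole study period", and that an independent committee analyses adverse events "to identify any unexpected adverse events or mortality in the CHM groups".

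No sentence says what counts as an evaluation, whether it must come after the first dose, or whether a death or an adverse event record is enough. No sentence brings back treated patients who were never evaluated.

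**The concern.** Exposure is settled once the first dose is taken. Being evaluated may not be: if the evaluation has to come after dosing, membership of the safety set depends partly on how the patient fares. The patients most likely to fail the condition are then those who die or leave soonest. A death that fails it disappears from the numerator and the denominator together, along with any non-fatal harm that preceded it.

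This deserves attention here because the disease has high short-term mortality, the herbal enema is confined to the first 7 days, the granules run for 8 weeks, and the scheduled safety tests have no stated time between baseline and the end of treatment. At stake is a safety-set death rate, and early adverse event rates, that look more favourable to CHM than the data warrant. It is also unsatisfactory that the meaning of the condition could be settled after the data are seen.

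**Working it through.** The plan gives no figure for this point, so there is nothing to reproduce. The check is a comparison of definitions, followed by an illustration.

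**1. The two sets compared.** Take a CHM patient who receives a dose and dies on day 2 with no scheduled post-dose assessment.

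| Set | Condition | Is this patient in? |
|---|---|---|
| Full analysis set | At least one dose | Yes |
| Safety set, baseline tests count | Took CHM, evaluated once | Yes, if baseline tests were done |
| Safety set, adverse event record counts | Took CHM, evaluated once | Yes, if an event was recorded |
| Safety set, scheduled post-dose assessment needed | Took CHM, evaluated once | No |

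The wording permits each of the last three rows. Under the final row the harm analysis is more selective than the efficacy analysis.

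**2. Direction.** With N treated, D deaths and k deaths removed as unevaluated, the change in the crude death rate is

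D/N − (D − k)/(N − k) = k(N − D) / [N(N − k)],

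which is positive whenever k > 0 and D < N. Removing unevaluated deaths can only lower the rate. Patients who leave alive and unevaluated would also drop out. Taken alone, that would raise the crude death rate, so the statement about direction applies to the deaths.

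**3. Inputs for an illustration.** Sample size states: "The proposed -12% superiority margin of 8-week mortality rate was chosen based on our previous results of 30.87% in the SMT group". It also gives 255 per group. Reading the 12 points as the expected effect, which is an inference, CHM mortality would be 30.87% − 12% = 18.87%. Deaths by week 8 among 255: 255 × 0.1887 ≈ 48 and 255 × 0.3087 ≈ 79.

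**4. Early deaths, assuming a constant hazard over 56 days.** h = −ln(1 − p)/56; deaths by day t = 255 × (1 − exp(−h·t)).

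| 8-week mortality | h per day | By day 3 | By day 7 |
|---|---|---|---|
| 18.87% | 0.00373 | 2.8 | 6.6 |
| 30.87% | 0.00659 | 5.0 | 11.5 |

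This gives about 3 to 5 deaths by day 3 and 7 to 12 by day 7. These are all deaths in the window; only those never evaluated would leave the set.

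**5. Effect on the safety-set death rate for a given k.**

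| k removed | From 48/255 = 18.8% | From 79/255 = 31.0% |
|---|---|---|
| 3 | 45/252 = 17.9% | 76/252 = 30.2% |
| 5 | 43/250 = 17.2% | 74/250 = 29.6% |
| 10 | 38/245 = 15.5% | 69/245 = 28.2% |

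The documents do not say which k applies, and k = 0 is possible.

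**The case against.** The strongest reply is that the plan never requires a post-dose evaluation. Safety is assessed before treatment as well as after, so a baseline assessment meets the literal wording. Adverse events are recorded throughout the study, only in-patients are eligible, and most are expected to stay in hospital for the 8 weeks. A dosed in-patient who deteriorates and dies would normally generate a safety record. For the exclusion to operate, the baseline tests, the adverse event record and the death itself must all fail to count as an evaluation, and nothing says that they do. This stands, and it makes the point conditional.

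It also stands that these deaths are not lost to the trial. The full analysis set needs only one dose, so each counts against CHM in the randomized comparison of transplant-free survival at week 12 (the per-protocol set, which requires all visits, would not keep them). Serious complications from week 1 to week 24 are a secondary outcome in their own right. The safety committee's review of mortality is not said to be limited to the safety set.

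What the reply does not do is fix the meaning of the condition. If baseline tests or any adverse event record suffice, the condition removes almost nobody and serves no purpose. If they do not, it removes the wrong patients. Neither the adverse event recording nor the committee's remit changes who belongs to the set.

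**Conclusion.** The point holds as a conditional one of small and unknown size. The definition can be read so that treated patients who die or leave before an evaluation fall out of the safety-set harm rates, and for deaths the bias then favours CHM. The effect is confined to the safety-set analysis.

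Two stronger conclusions are tempting, and the documents support neither. A reader might infer that early CHM deaths are definitely excluded; that depends on a post-dose requirement which the text does not contain. A reader might also infer that most of the 48 to 79 deaths by week 8 would go, because the only scheduled assessment after baseline follows treatment; that sets aside the adverse event recording that runs through the whole study. Nor do the documents give any basis for choosing a share of deaths that would go unevaluated.

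The 7 to 12 deaths by day 7 rest on a constant hazard, on 18.87% as an inferred CHM rate, and on all 255 patients being dosed. They show how many early deaths might be exposed to the rule, not how many would be lost.

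**What to change.** In Data management and Statistical methods, delete the requirement of at least one safety evaluation. Define the safety set by receipt of at least one dose of study treatment, as the full analysis set already is, and state that all recorded deaths and adverse events in these patients are counted whether or not a safety visit took place.

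The cost is one edited sentence. No extra visits, data or patients are needed. The same sentence also limits the safety set to CHM takers, which leaves it without a control group. That is a separate matter, but a definition by study treatment in either arm would deal with both in one edit.

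### The safety set contains only patients who took CHM, so adverse events and safety tests outside the efficacy outcomes have no planned SMT comparator

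*Combined protocol and SAP*

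**What the plan says.** The section Data management and Statistical methods defines three analysis sets. For efficacy: "The randomized subjects who take at least one dose of CHM or SMT constitute the full analysis set (FAS", together with a per-protocol set of those completing all visits. For safety: "Subjects who have taken the CHM and been evaluated the safety at least once constitute the safety set (SS". The plan then assigns the safety set, and no other, to safety evaluation.

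The next paragraph of that section gives generic tests: "Comparison of the two groups is conducted for the continuous variables" by t-test, and for categorical variables or rates by chi-square. It does not mention safety.

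Under Standard medical treatment, CHM by any route is prohibited in the SMT group. Under Criteria for discontinuing or modifying allocated interventions, a participant may ask to change intervention, and such changes are recorded and analysed by intention to treat.

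Under Safety outcomes, vital signs, physical examination, ECG and some laboratory tests are assessed before and after treatment, and "adverse events are also recorded in a predesigned case report form (CRF) through the whole study period". Neither is limited to one arm. An independent committee reviews the incidence and severity of adverse events "to identify any unexpected adverse events or mortality in the CHM groups".

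Some harm-related outcomes appear instead under Secondary outcomes: "the incidence of serious complications (including infections, encephalopathy, HRS, and gastrointestinal bleeding) from week 1 to week 24", and "the influence on liver function assessed by MELD score (involving levels of serum bilirubin, creatinine, INR and sodium) at week 12", with Child-Pugh at the same time point.

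**The concern.** All patients have acute-on-chronic liver failure, and many will have adverse events and abnormal tests from the disease alone. The proportion of CHM patients with an event therefore says little about CHM unless it is set against the proportion in concurrent SMT patients. A programmer who follows the definition would produce safety tables with no control column, even though the SMT data appear to be collected.

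The trial's title promises safety as well as effectiveness, and the regimen adds multi-herb granules for 8 weeks and an enema for 7 days. The randomised comparison is the best evidence the trial can offer on harm. For the events that sit only in the safety set, the plan as written leaves that comparison out. The documents give no expected adverse event rate without CHM that could stand in for it; the only SMT rate stated is 8-week mortality, under Sample size.

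**Working it through.** **Who can be in each set**

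| Set | Treatment named | Assigned use | SMT patient treated per protocol |
|---|---|---|---|
| Full analysis set | CHM or SMT | Efficacy | Included |
| Safety set | CHM only | Safety | Cannot be included |

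The safety set therefore holds at most 255 CHM-allocated patients and no SMT patients treated as planned. An SMT patient who switches to CHM would enter it, but as a CHM-exposed patient and not as a comparator. With SMT included, the set would hold at most 255 + 255 = 510.

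**What has a comparator and what does not**

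- Compared between arms as efficacy outcomes: transplant-free survival, the listed serious complications, and MELD and Child-Pugh at week 12. The two scores bring in bilirubin, creatinine, INR, sodium and albumin.
- No planned comparator: other adverse events, ECG, vital signs, routine blood counts and urine tests.

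**What a CHM-only rate can show**

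The plan gives no safety figure to reproduce. The arm size of 255 is taken as stated under Sample size and serves only to scale the example. The event counts are assumptions.

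*CHM alone.* 38/255 = 0.149. The Wilson interval is [p + z²/2n ± z√(p(1−p)/n + z²/4n²)] / (1 + z²/n). With n = 255 and z = 1.96 this is (0.1566 ± 0.0444)/1.0151, or 11.1% to 19.8%.

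*With SMT at 13/255 (5.1%).* Difference 0.1490 − 0.0510 = 0.098. SE = √(0.1490×0.8510/255 + 0.0510×0.9490/255) = 0.0262. The Wald 95% CI is 0.047 to 0.149.

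*With SMT at 38/255.* Difference 0. SE = √(2×0.1490×0.8510/255) = 0.0315. The 95% CI is −0.062 to 0.062.

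The first SMT rate would indicate harm and the second would not. The CHM-only table is identical in both.

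**What a by-arm table could show**

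Power for a two-sided 5% test of two proportions is Φ[(Δ − 1.96·s₀)/s₁] plus the negligible opposite tail. Here s₀ = √(2p̄(1−p̄)/n), s₁ = √((p₁(1−p₁) + p₂(1−p₂))/n) and n = 255. For example, with SMT 5% and CHM 10%, s₀ = 0.02333 and s₁ = 0.02322, so Φ(0.184) = 0.573. The half-width of the 95% CI at equal rates is 1.96√(2p(1−p)/255).

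| Assumed SMT rate | Power, 5-point excess | Power, 10-point excess | CI half-width, equal rates |
|---|---|---|---|
| 5% | 57% | 97% | 3.8 points |
| 10% | 40% | 89% | 5.2 points |
| 20% | 27% | 74% | 6.9 points |
| 30% | 23% | 66% | 8.0 points |

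With 229 per arm (255 × 0.9, rounded down) the 10-point powers are 95, 85, 70 and 61%. An excess of about 10 points would usually be seen; one of 5 points often would not.

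**The case against.** The strongest reply is that this is a drafting slip. The full analysis set sentence names both treatments, the generic test sentence covers two-group comparison of rates without restricting it to efficacy, and adverse events are recorded without restriction by arm. A sensible analyst might tabulate both arms anyway. The slip is plausible, but the generic sentence does not redefine the set assigned to safety, and nothing else in the documents corrects it.

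A second reply is that the most serious harms are already controlled. This stands and limits the point. A reader might infer that the trial has no controlled safety information at all, or might size the problem by the deaths expected in the CHM arm. The documents support neither. Deaths and the serious complications are compared between arms as efficacy outcomes, and several blood values are compared through MELD and Child-Pugh. In addition, Sample size states a superiority margin, not an expected CHM mortality, so a CHM death count would itself be an inference.

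A reader might also infer that the safety committee is denied SMT data, or that the stopping rule ("The study will end at once if severe adverse events associated with CHM occurs") must operate without a control group. The documents do not say so. The committee's remit looks for signals among CHM patients, but it is not tied to the safety set, and case-by-case attribution remains possible. The gap shown by the text is in the planned safety analysis.

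**Conclusion.** The concern holds in this limited form and should be corrected before the analysis. The only set assigned to safety excludes SMT patients treated per protocol, so part of the safety evaluation has no concurrent comparator.

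This conclusion rests on the definitions alone and needs no assumed rate. The assumed rates only illustrate its size: the same 14.9% in the CHM arm is compatible with an excess of 9.8 points or with none. The illustration assumes 255 analysed patients per arm and no switching. The documents do not give the number of switchers, and it cannot be estimated from them.

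**What to change.** 1. Define the safety set as all randomised patients who received at least one dose of CHM or SMT and had at least one safety assessment. A recorded adverse event or a death should count as an assessment, so that early deaths are not dropped.
2. Report adverse events and safety tests by arm, with risk differences and 95% CIs.
3. Analyse by treatment received (any CHM versus SMT alone) and show the as-randomised table alongside. The second table keeps faith with the intention-to-treat rule for treatment changes. It also guards against a weakness of the first: patients who die before they could switch stay in SMT alone.
4. List SMT-allocated patients who switch to CHM separately, distinguishing events before the switch from events after it, so that pre-switch events are not read as CHM events.
5. Make the by-arm tables available to the existing safety committee.

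The cost is one changed definition, an SMT column and a short listing. No new visits are implied, because the recording described under Safety outcomes is not limited to one arm. Two limits remain. Precision for small excesses is poor, as the power table shows. No placebo is described, so patients and staff may report adverse events differently by arm, and the tables should carry a note saying so.

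### Week-12 MELD and Child-Pugh are assigned a plain t-test with no baseline score in the analysis, which gives up precision that baseline adjustment would recover almost free

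*Combined protocol and SAP*

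**What the plan says.** All references are to the Combined protocol and SAP.

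- **Outcomes.** Secondary outcomes lists "the influence on liver function assessed by MELD score (involving levels of serum bilirubin, creatinine, INR and sodium) at week 12" and, also at week 12, "the influence on liver function assessed by Child-Pugh score". Neither is defined as a level at week 12 or as a change from baseline.
- **Method.** Data management and Statistical methods says: "Comparison of the two groups is conducted for the continuous variables with" a t-test. No covariate, change score or ANCOVA is named for these two scores.
- **Other models.** The regressions serve other questions: "Cox proportional hazards regression model will be adopted to determine the prognostic factors associated with transplant-free survival", and logistic regression is for liver-related complications.
- **Analysis sets and missing data.** "An efficacy assessment will be analyzed using FAS and PPS based on the principle of ITT". The PPS is limited to patients who attend every visit. "The last observation carried forward approach was used for missing values". The plan does not say whether a score that is absent because of death or transplant counts as a missing value.
- **Baseline data.** Bilirubin and coagulation are obligatory items in Diagnostic criteria, which also mentions ascites and encephalopathy. Safety outcomes says that "renal function will be assessed before and after treatment". Entry sodium and albumin are not explicitly listed.

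**The concern.** Both outcomes ask how treatment influences liver function, and each patient's starting score is largely known. Patients enter with widely differing severity, and part of the spread in week-12 scores will simply reflect where they began. A two-group t-test on week-12 scores leaves that spread in the error term. The confidence intervals are then wider than the collected data require, for the only two secondary outcomes that measure liver function directly.

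Mortality raises a second, more limited issue. If one arm keeps more of the sicker patients alive, survivors in the two arms no longer have the same baseline mix, and an unadjusted comparison restricted to them mixes that difference with the treatment effect.

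**Working it through.** **Plan's own figures.** The plan gives no SD, effect size or power for MELD or Child-Pugh, so there is nothing to reproduce for these outcomes. The 255 per group under Sample size concerns 8-week mortality. Reading the 12 points as the expected difference (30.87% against 18.87%), a two-sided 5% test with pooled variance and 80% power needs 203 per group, and 203/0.9 gives 226, not 255. That mismatch does not bear on this point. I use 255 only as the planned arm size.

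**Step 1: precision against a t-test on week-12 scores.** With correlation ρ between baseline and week-12 score in the patients analysed, ANCOVA multiplies the residual variance by 1 − ρ² and the standard error by √(1 − ρ²). A comparison with 80% power by t-test then has power Φ[(1.960 + 0.842)/√(1 − ρ²) − 1.960].

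The last column below is the MELD difference detectable with 80% power: 2.8016 × 6 × √(1/176 + 1/207) = 1.72 points by t-test, times √(1 − ρ²) for ANCOVA. It assumes a week-12 SD of 6. It takes survivors as 255 × 0.6913 ≈ 176 (SMT) and 255 × 0.8113 ≈ 207 (CHM), using the 8-week rates with no other losses.

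| ρ (assumed) | 1 − ρ² | Variance cut | SE ratio | Power, from 80% | Detectable difference, from 1.72 |
|---|---|---|---|---|---|
| 0.3 | 0.91 | 9% | 0.954 | 83.6% | 1.64 |
| 0.5 | 0.75 | 25% | 0.866 | 89.9% | 1.49 |
| 0.7 | 0.51 | 49% | 0.714 | 97.5% | 1.23 |

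**Step 2: precision against a t-test on change.** With SDs s₀ (baseline) and s₁ (week 12), change has variance s₁² + s₀² − 2ρs₀s₁ and ANCOVA has s₁²(1 − ρ²). The first minus the second is (s₀ − ρs₁)², which is never negative. With equal SDs the ratio of ANCOVA to change is (1 + ρ)/2, that is 0.65, 0.75 and 0.85, so ANCOVA cuts the variance by 35%, 25% and 15%. Once baseline is in the model, taking the week-12 score or the change as response gives the same treatment estimate.

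**Step 3: what adjustment does when arms differ in deaths.** This was simulated with 255 per arm, mortality 30.87% against 18.87%, and no treatment effect on the score itself (1,500 trials per setting). Assumed values:
- MELD SD 5 at baseline and 6 at week 12, with ρ from 0.3 to 0.7.
- Week-12 scores centred on 15, and last scores before death centred on 32.
- Log-odds of death rising by 0.5 or 1 per SD of baseline and, in one setting, also by 1 per SD of unmeasured severity.

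Results are CHM minus SMT in MELD points, so a positive value counts against CHM.

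| Who is analysed | t-test | ANCOVA |
|---|---|---|
| Survivors, death depends on baseline only | +0.09 to +0.37 | −0.02 to +0.01 |
| Survivors, death also depends on unmeasured severity | +0.65 to +0.69 | +0.40 to +0.56 |
| All patients, last score of the dead carried forward | −1.80 to −2.11 | −1.81 to −2.12 |

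In the survivor analyses, baseline MELD was 0.28 to 0.48 points higher in CHM. The first row follows from this: at ρ = 0.5 the slope is 0.5 × 6/5 = 0.6, and 0.6 × 0.47 = 0.28, against a simulated +0.29. The last row is the mortality difference passing into the score: 0.12 × (32 − 15) = 2.04 points. Adjustment leaves it in place, although it still narrows the spread of the estimate (for example from 0.89 to 0.75 at ρ = 0.5).

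**The case against.** The strongest reply is that an unadjusted t-test is valid under randomisation, so leaving out baseline costs efficiency only. That stands. These are also two of five secondary outcomes, and the gain depends on a correlation that the plan does not report. All of that is right and limits the weight of the point.

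A second reply is that influence on liver function may mean change from baseline, in which case the t-test would already use the starting score. The plan defines neither reading, so it cannot be said to compare raw week-12 levels. Step 2 shows that the recommendation does not depend on which was meant.

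A reader might go further and infer that the t-test is biased against CHM and will understate its benefit because CHM keeps sicker patients alive. The documents do not support that. The inference requires the dead to be left out, as in the PPS or a survivors-only analysis. Efficacy is also analysed in the FAS with LOCF, and whether that rule covers deaths is not stated. If it does, the distortion runs the other way, towards the arm with fewer deaths. Nor is adjustment a cure: it removes the survivor imbalance fully only if death depends on the measured baseline score alone.

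**Conclusion.** The point holds as a loss of precision. The plan names a t-test and no baseline adjustment for week-12 MELD and Child-Pugh. Against a t-test on week-12 scores, adjustment would remove about 9% to 49% of residual variance for assumed correlations of 0.3 to 0.7, and it is never less precise than a t-test on change, apart from the negligible cost of estimating one slope. The relevant correlation is the one among the patients analysed, which selection by death can lower.

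Bias is a secondary matter, and its direction cannot be fixed from the documents. In survivors or the PPS, ANCOVA partly corrects a case-mix difference. It does not correct for unmeasured severity or for carried-forward scores of the dead. The MELD-point figures in Step 3 illustrate direction only, since their SDs, means and severity effects are assumed.

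This is a cheap improvement to two secondary outcomes. The primary outcome is not affected.

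**What to change.** In Data management and Statistical methods, replace the t-test for week-12 MELD and Child-Pugh with linear regression of the week-12 score on arm and the patient's own score at randomisation. Report the adjusted mean difference with its 95% CI. In Secondary outcomes, state that the outcome is the week-12 score adjusted for baseline, which settles whether level or change was meant.

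Alongside this, state how deaths and transplants enter both outcomes instead of leaving them to LOCF. Two options are an explicitly named survivor estimand or a rank analysis that places death worst, with transplant given a stated position. Say which analysis leads. Baseline adjustment alone does not close this gap.

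The cost is SAP wording, ideally agreed before any comparison by arm is seen. Entry sodium and albumin would need adding to the baseline blood tests if they are not already taken routinely. No change to sample size or visits is needed.
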